## Hypotheses

Hypothesis 1: When centers must present information on their transplant success rate only, lay evaluators will respond by selecting hospitals with higher transplant success. However, if information presented on transplant outcomes is stratified by the number and quality of donors used, or displayed in addition to total survival rates, then participants will respond by selecting hospitals with higher organ acceptance rates rather than the hospital with higher transplant outcomes. Hypothesis 1a: Preference for the non-selective transplant center will be lower (than for the selective center) in condition 1 (baseline: combined transplant survival only), compared to the other 4 conditions. That is, a higher proportion of participants will prefer the non-selective center over the selective center in conditions 2, 3, 4, and 5, relative to condition 1. Hypothesis 1b: There will be a main effect of viewing total survival, such that in conditions 2 and 4 (when total survival is displayed), participants will prefer the non-selective center over the selective center, relative to the baseline condition 1. Hypothesis 1c: There will be an additional main effect of viewing stratified transplant survival, such that in conditions 3 and 4 (when transplant survival is stratified by number and quality of donor hearts accepted at each center) participants will prefer the non-selective center over the selective center, relative to the baseline condition 1. Hypothesis 1d: There will be an interaction effect between total and stratified transplant survival, such that when participants view both stratified transplant survival and total survival outcomes together, preference for the non-selective center is higher relative to preferences at baseline (condition 1), but not higher relative to preferences when total survival information is added to the display (condition 2) or stratified transplant survival

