only is displayed (condition 3). Hypothesis 2: There will be an indirect (mediated) effect of providing participants with information about stratified transplant survival or total survival; this information will lead to higher preference for the non-selective hospital by leading participants to think that the chances a patient at either hospital will "get a heart at all" is a more important factor in their decision (about which hospital is a better choice for patients). Specifically ratings of importance (0-100 continuous scale) for the item "likelihood of getting any heart" will differ across conditions 1-4 such that "getting any heart" will be rated lower in condition 1 than in the other three conditions. Furthermore, ratings on this item will be associated with choice, such that higher ratings will be associated with choice of the non-selective center. Hypothesis 3: Participants who view total survival only (condition 5) will show a higher preference for the non-selective center relative to participants in the baseline combined transplant survival display (condition 1) such that the effect of displayed total survival alone will be similar to the effect of displaying both stratified transplant survival and total survival outcomes together (as in condition 4).

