### Study design

We have a between-subjects design in which participants are randomized to one of five information conditions. In each condition, they make a choice between two hospitals (one with a non-selective donor acceptance strategy, and another with a more selective donor acceptance strategy). The first four conditions (1-4) will be included in our main analysis, which is a 2x2 design with 2 factors (total survival and transplant survival) and 2 levels per factor: (i) Total survival: "total not displayed" = reference level, in which only transplant survival rate (and not total or waitlist survival) is shown "total displayed" = transplant survival is displayed along with the overall survival rate at each center, which is computed from survival rates of both transplant and waitlist patients (ii) Transplant survival: "combined": reference level, in which transplant survival rate is not stratified by number and quality of donor hearts accepted at each center "stratified": transplant survival rate stratified into patients who received excellent donor organs and patients who received less than optimal donor organs The additional fifth condition, in which only total survival outcomes (and no transplant survival outcomes) are displayed, will be included in the study and analyzed separately.

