### Sample size rationale

Sample sizes were calculated to yield at least 90% power to detect a 15 percentage point difference (e.g., 45% vs. 60%) between baseline condition 1 and the other 4 conditions, with  $\alpha=0.05$  (GPower 3.1.9.4).

Stopping rule

Participants will be recruited until a sample size of 1000 is achieved.

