## Variables

Manipulated variables

We will manipulate how transplant center outcomes are presented. Different components of the same outcome statistics for two transplant centers will be varied over five different conditions. (1) Condition 1 ("baseline" condition): view only combined transplant survival (e.g. transplant survival rate not stratified by number and quality of donor hearts accepted at each center) (2) Condition 2: view combined transplant survival + total survival (e.g. overall survival rate at each center, computed from survival rates of both transplant and waitlist patients) (3) Condition 3: view only stratified transplant survival (e.g. transplant survival rate stratified into patients who received excellent donor organs and patients who received less than optimal donor organs) (4) Condition 4: view stratified transplant survival + total survival (5) Condition 5: view only total survival The first four conditions (1-4) will be included in our main analysis, which is a 2x2 design with 2 factors (total survival and transplant survival) and 2 levels per factor: (i) Total survival: "total not displayed" = reference level, in which only transplant survival rate (and no total or waitlist survival) is shown "total displayed" = transplant survival is displayed along with the overall survival rate at each center, which is computed from survival rates of both transplant and waitlist patients (ii) Transplant survival: "combined": reference level, in which transplant survival rate is not stratified by number and quality of donor hearts accepted at each center "stratified": transplant survival rate stratified into patients who received excellent donor organs and patients who received less than optimal donor organs The additional fifth condition, in which only total survival outcomes (and no transplant survival outcomes) are displayed, will be included in the study and analyzed separately.

Measured variables

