
importance of "getting any heart" to increase preference for the non-selective hospital. If the ACME is non-significant, we will identify where the causal path breaks down. To test Hypothesis 3, we will use a binomial logistic regression analysis with a contrast test for a difference in effect size between conditions 4 and 5.

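### Hypothesis 3 predicts that condition 5 beats condition 1 and is similar to condition 4, but its one stated test, a 4-versus-5 difference contrast, can establish neither; the 5-versus-1 comparison in Hypothesis 1a also has no stated test

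*Combined protocol and SAP*

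**What the plan says.** Hypothesis 3 (Hypotheses section) makes two predictions. The first is directional: "condition 5) will show a higher preference for the non-selective center relative to participants in the baseline combined transplant survival display (condition 1"). The second is about closeness: "the effect of displayed total survival alone will be similar to the effect of displaying both stratified transplant survival and total survival outcomes together", the latter being condition 4.

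The Analysis Plan gives one sentence to this hypothesis: "we will use a binomial logistic regression analysis with a contrast test for a difference in effect size between conditions 4 and 5". The Inference criteria section supplies one rule, significance at p=0.05 against a null hypothesis. There is no equivalence margin, confidence-interval criterion or other definition of similar.

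Hypothesis 1a also involves condition 5. It predicts a higher proportion choosing the non-selective center "in conditions 2, 3, 4, and 5, relative to condition 1". The Sample size rationale likewise refers to a difference "between baseline condition 1 and the other 4 conditions". But the Analysis Plan assigns Hypotheses 1a to 1d to a logistic model with two binary factors and their interaction, and the Study design section limits that analysis: "The first four conditions (1-4) will be included in our main analysis". Condition 5 is to be analyzed separately.

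**The concern.** The stated analyses do not answer the stated hypotheses in three places.

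- **Similarity of 4 and 5.** A significant contrast would contradict this part of Hypothesis 3. No result of the contrast could support it, because failing to find a difference does not show that the difference is small. Without a rule, the reading of a null result would be chosen after the data are seen.
- **5 over 1 in Hypothesis 3.** This is the first half of the hypothesis, and no contrast is named for it.
- **5 over 1 in Hypothesis 1a.** The model assigned to 1a contains no condition 5 data.

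At stake is whether the report can say that showing total survival alone works, and works about as well as the fuller display. A total-survival-only display that had lost much of the effect could be described as similar, and Hypothesis 1a could be declared supported without its condition 5 component having been tested.

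**Working it through.** **Inputs from the plan.** About 200 participants per condition (Sample size); 45% versus 60% as the example rates, alpha 0.05 and at least 90% power (Sample size rationale). Sidedness is not stated. **Assumptions of this review:** exactly 200 analyzed per arm, condition 1 at 45%, condition 4 at 60%, and condition 5 at the values shown.

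**1. The plan's own figure.** For 200 versus 200 at 45% versus 60%, the pooled rate is 0.525. The null SE is sqrt(2×0.525×0.475/200) = 0.0499 and the alternative SE is sqrt((0.45×0.55+0.60×0.40)/200) = 0.0494. Two-sided power is Φ((0.15−1.96×0.0499)/0.0494) = Φ(1.056) = 85.4%. One-sided it is 91.5%. Condition 1 against the other four pooled (200 versus 800) gives 96.9% two-sided. So 90% is reached one-sided or pooled, but not for a two-sided pairwise test. The plan does not say which was meant.

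**2. What the 4-versus-5 contrast tests.** Write θ for the log-odds of choosing the non-selective center. If effects are measured against condition 1, the difference in effects is (θ4−θ1)−(θ5−θ1) = θ4−θ5. Condition 1 cancels, so the contrast does not test 5 over 1.

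**3. Whether the 2x2 model can supply 5 versus 1.** It cannot. Its displayed level for total survival is defined as "transplant survival is displayed along with the overall survival rate at each center", and its other factor is combined or stratified transplant survival. Condition 5 is the one "in which only total survival outcomes (and no transplant survival outcomes) are displayed", so it has no level on that second factor. The 4-versus-1 comparison can be formed in the 2x2 model as total + stratified + interaction, although the plan does not list it.

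**4. What would follow if non-significance were read as similarity.** Take condition 5 at 52.5%, half of condition 4's 15-point effect. The pooled rate is 0.5625, the null SE is sqrt(2×0.5625×0.4375/200) = 0.0496, and the alternative SE is sqrt((0.24+0.525×0.475)/200) = 0.0495. Power of the contrast is Φ((0.075−1.96×0.0496)/0.0495) = Φ(−0.449) = 33%, so it is non-significant 67% of the time.

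The range below comes from simulation (1,000,000 runs, Wald tests on risk differences, condition 1 at 45%):

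| True rate, condition 4 / condition 5 | 4 vs 5 non-significant | ...and 5 over 1 significant |
|---|---|---|
| 60 / 60 | 95% | 82% |
| 60 / 55 | 83% | 48% |
| 60 / 52.5 | 67% | 28% |
| 60 / 50 | 48% | 13% |
| 45 / 45 (no effect anywhere) | 95% | 2% |

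These become error rates only once a gap is declared dissimilar, and the plan gives no margin for any row.

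**5. What 200 per arm can say about similarity.** With both arms at 60%, SE = sqrt(2×0.24/200) = 0.049, so the 95% confidence interval half-width is 1.96×0.049 = 9.6 points. Equivalence power (two one-sided 5% tests, true difference zero) is 2Φ(m/0.049−1.645)−1. At m = 10 points this is 2Φ(0.396)−1 = 31% (30% by simulation). At m = 15 points it is 2Φ(1.417)−1 = 84%, but 15 points is the whole effect the study is sized to detect.

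**6. How Hypothesis 1a would be judged.** With conditions 2 to 5 all at 60%, one two-sided contrast against condition 1 succeeds 86% of the time in simulation, all four succeed 66%, and one pooled contrast succeeds 97%. If condition 5 has no effect (45%) and conditions 2 to 4 are at 60%, the pooled rate of the four is (3×60+45)/4 = 56.25%. Its difference from condition 1 is 11.25 points, with SE sqrt(0.2475/200+0.5625×0.4375/800) = 0.0393. The chance of significance is Φ(0.1125/0.0393−1.96) = Φ(0.90) = 82%. A significant pooled contrast therefore does not show 5 over 1.

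**The case against.** The strongest reply is that a difference test is a legitimate way to put Hypothesis 3 at risk, and that the plan nowhere claims that a null result proves similarity. That is right. A reader might infer that the authors intend to equate non-significance with similarity; the text does not say so. The figures in step 4 describe a rule that the plan leaves open, not one that it adopts. What remains is that the second part of the hypothesis has no rule under which it could be supported.

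It can also be said that 5 versus 1 is nearly specified. The hypothesis is stated relative to condition 1, the direction, outcome coding and alpha are fixed, and a logistic model referenced to condition 1 would give the coefficient at once. This limits the analytic freedom and makes the repair easy. It does not supply the model, because the only contrast named is one from which condition 1 drops out.

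A reader might go further and suppose that Hypothesis 1a could be claimed on any one of its four comparisons. The wording joins the conditions with an and, so only a judgment on each contrast or on a pooled contrast is plausible.

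Finally, the reach is limited. Condition 5 lies outside the main analysis, and it would be wrong to infer that the 2x2 results are compromised. If 5 over 1 is required as well, false support for Hypothesis 3 when no display has any effect is about 2%.

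**Conclusion.** The point holds and should be fixed. The analysis stated for Hypothesis 3 can contradict its similarity part but cannot support it, and does not test 5 over 1. The model assigned to Hypothesis 1a excludes the condition 5 data that the hypothesis needs. This is more than missing detail, because following the plan to the letter leaves those parts unanswered.

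The size depends on a reading the plan does not fix. If non-significance were taken as similarity, a condition 5 that kept only half of condition 4's effect would pass the contrast 67% of the time, or 28% with 5 over 1 also significant. These figures assume 200 analyzed per arm and rates of 45%, 60% and 52.5%; the first two rates are the plan's example and the third is an assumption of this review. Whether a 7.5-point gap is dissimilar cannot be settled from the documents. Hypotheses 1b to 1d, as tested by the 2x2 coefficients, do not depend on this point.

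**What to change.** - Keep the 2x2 interaction model on conditions 1 to 4 for Hypotheses 1b to 1d.
- Add one logistic model with a five-level condition factor and condition 1 as reference. Name its 5-1 contrast (two-sided 0.05, in the predicted direction) as the test of the first part of Hypothesis 3 and of the condition 5 part of Hypothesis 1a. Take 2-1, 3-1 and 4-1 from the same model.
- For the second part of Hypothesis 3, report the 4-5 risk difference with its 95% confidence interval and state that non-significance will not be read as similarity. Reword this part as an estimated difference unless a justified margin, with its power, is stated in advance.
- State whether Hypothesis 1a is judged on each contrast or on a pooled contrast. If pooled, say that it does not establish 5 over 1. If individual contrasts are to be claimed separately, state the multiplicity rule.

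The cost is wording, one extra model and one interval, with no added participants. There are two downsides. Similarity is unlikely to be claimable at a tight margin: power is about 30% at 10 points, and 80% would need 2×0.24×((1.645+1.282)/0.10)² ≈ 412 per arm in conditions 4 and 5. If the sponsor chooses to require all four contrasts for Hypothesis 1a, power is about 66% at 45% versus 60% with 200 per arm. That rule is an option for the sponsor, not a requirement of this point.

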#### *No files selected*

##### Transformations

Logistic regression analysis: The categorical predictor "total survival displayed" will be dummy coded (0=not displayed, 1=displayed), with 'not displayed' as the reference category. The categorical predictor "transplant survival stratified" will be dummy coded (0=not stratified, 1=stratified), with 'stratified' as the reference category. The outcome variable "choice of hospital" will be dummy-coded (0=selective hospital, 1=non-selective hospital). The reference category is 'selective hospital'. Mediation analysis: The categorical predictor "total survival displayed" will be dummy coded (0=not displayed, 1=displayed), with 'not displayed' as the reference category. The categorical predictor "transplant survival stratified" will be dummy coded (0=not stratified, 1=stratified), with 'stratified' as the reference category. The categorical interaction term "total survival displayed\*transplant survival stratified" will be dummy coded (0=total and stratified information not displayed together, 1=both total and stratified information displayed together), with 'both' as the reference category. The continuous mediator variable "get any heart" will be mean-centered for each analysis. The outcome variable "choice of hospital" will be dummy-coded (0=selective hospital, 1=non-selective hospital). The reference category is 'selective hospital'.

##### Inference criteria

We will use the standard  $p=0.05$  criteria for determining if the results are significantly different from those expected if the null hypothesis were correct.

##### Data exclusion

(1) Participants on mTurk will not be allowed to participate if they fail to pass the initial "bot screening", a multiple-choice question that asks, "What phone number should you dial when there is an emergency?" The obvious correct response in this screening question is "911", so participants who select one of the incorrect responses (i.e. "1-800-ANTIBOT", "1-877-MTURKER", "123") are filtered out and not allowed to complete the survey. (2) Participants on mTurk will be allowed to participate, but excluded from data analysis, if they submit a nonsense response to the free-response question which reads, "In your own words, why do you think patients should choose the hospital you picked?" This question takes place after the participant has viewed the choice stimuli and selected their response. If participants input nonsense in the text response box, they will be permitted to complete the survey and paid, but filtered out from the data analysis. In addition, two attention checks will be used. The data will be analyzed with all participants, and with only the participants who pass both of these attention checks.

##### Missing data

If a participant does not complete the entire survey, they will not be included in the analysis.

##### Exploratory analysis

#### *No response*

# Other

Other

*No response*
